8.9.2 Laboratory Parameters

Clinical laboratory values (in SI units) at each assessment time point will be summarized for laboratory parameters in hematology, chemistry and urinalysis. The frequency and percentage of subjects who experience abnormal clinical laboratory results (i.e. outside of reference ranges) and/or clinically significant abnormalities after study drug administration will be presented by laboratory measurement.

The clinical laboratory parameters include the following:

- Chemistry: Alanine aminotransferase (ALT), Alkaline phosphatase, Aspartate aminotransferase (AST), Bilirubin (total), Blood urea nitrogen (BUN), Calcium, Chloride, Serum creatinine, Gamma-glutamyl transpeptidase (GGT), Serum glucose, Potassium, Protein (albumin and total), Sodium, Creatine Kinase
- Hematology: Hematocrit, Hemoglobin, Platelet count, Red blood cell (RBC) count, White blood cell (WBC) count
- Urinalysis: Appearance, Color, pH, Specific gravity, Ketones, Protein, Glucose, Pregnancy test (if applicable)

Hy's Law criteria will be applied against test results. Subjects with serum total bilirubin $>2 \times$ ULN and ALT or AST $>3 \times$ ULN will be considered positive for Hy's law status. Results will be presented in shift tables. For Hy's Law, shift tables will be produced:

- Hy's Law negative at baseline, remaining Hy's Law negative throughout the study
- Hy's Law negative at baseline, becoming Hy's Law positive at any point during the study
- Hy's Law positive at baseline and Hy's Law negative throughout the study
- Hy's Law positive at baseline and Hy's Law positive at any point during the study

A data listing of all subjects who are Hy's Law positive will be produced.

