7.5.4 Safety Measures & General Assessments

General assessments include medical history and demographics. Safety will be evaluated by the incidence, frequency, severity, and relatedness of AEs and SAEs, including clinically significant changes from baseline to scheduled time points in vital signs, weight, physical examination, and clinical laboratory evaluations. Pregnancy testing (or pregnancy of partner), suicidal ideation and behavior assessments, and concomitant medications will also be monitored. Refer to the Study Reference Manual for additional details.

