7.6.3 Safety Analyses

The primary safety analysis will evaluate the incidence and frequency of AEs and SAEs, including clinically significant changes in safety parameters throughout the Treatment Extension Period. The incidence and frequency of AEs will be summarized by System Organ Class and Preferred Term, relationship to study drug, and severity. No formal hypothesis testing will be performed.

Safety will be evaluated by the incidence, frequency and severity of AEs and SAEs, including clinically significant changes from baseline to scheduled time points in:

- Vital signs and weight
- Physical examination
- Clinical laboratory evaluations
- Pregnancy testing
- Suicidal ideation and behavior assessments
- Concomitant medications

The analyses of safety will be performed on the safety analysis population.

All AEs will be coded using the Medical Dictionary for Regulatory Activities (MedDRA). The incidence and frequency of AEs will be summarized by System Organ Class (SOC), Preferred Term (PT), relationship to study drug, and severity. All reported AEs with onset

during treatment (i.e. treatment-emergent AEs) will be included in the analysis. For each AE, the percentage of subjects who experienced at least 1 occurrence of the given event will be summarized by treatment group. The numbers (frequency) and incidence rates of AEs and SAEs will be summarized during exposure to UX007 throughout the study. Special attention will be given to those subjects who died, discontinued treatment due to an AE, or experienced a SAE (e.g. summaries, listings, and narrative preparation, as appropriate).

Clinical laboratory data will be summarized by the type of laboratory test. The frequency and percentage of subjects who experience abnormal clinical laboratory results (i.e. outside of reference ranges) and/or clinically significant abnormalities after study drug administration will be presented for each clinical laboratory measurement.

Changes in findings from physical examinations will be tabulated and listed for each subject by examination category. If there are examination findings that change in more than one subject, these will be tabulated in a separate table and expressed as the number of subjects with the change out of the total.

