4.1 Safety Endpoints

- Subject incidence and severity of Adverse events (AEs) and serious adverse events (SAEs)
- Subject incidence of treatment related AEs, AEs leading to discontinuation, fatal AEs, and Gastrointestinal AEs using the standardized MedDRA query (SMQ) as listed in [Appendix C](#).
- Prior and concomitant medication
- Observed value of vital signs and weight during the study
- Observed value of clinical laboratory test results and percentage of subjects who experience abnormal clinical laboratory results (i.e. outside of reference ranges) and/or clinically significant abnormalities
- The number and percentage of subjects with suicidal ideation and behavior assessment as measured by the Columbia Suicide Severity Rating Scale (C-SSRS)
- Physical examination
- Pregnancy testing if applicable

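### The laboratory abnormality percentages take no account of baseline, so the table cannot separate pre-existing abnormalities from new or worsened ones

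*SAP*

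**What the plan says.** SAP 8.9.2 gives two general laboratory outputs. One is a summary of values at each assessment time point. The other is a count of subjects: "The frequency and percentage of subjects who experience abnormal clinical laboratory results (i.e. outside of reference ranges", which continues "and/or clinically significant abnormalities after study drug administration will be presented by laboratory measurement". The endpoint in SAP 4.1 matches it: "Observed value of clinical laboratory test results and percentage of subjects who experience abnormal clinical laboratory results". Protocol 7.6.3 uses the same rule ("i.e. outside of reference ranges) and/or clinically significant abnormalities after study drug administration will be presented for each clinical laboratory measurement"). None of the three attaches a condition on the baseline value.

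The only laboratory output tied to baseline is for liver safety: "For Hy's Law, shift tables will be produced", followed by four categories of Hy's Law status.

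The protocol also describes safety evaluation in terms of AEs and SAEs, including "clinically significant changes from baseline to scheduled time points in vital signs, weight, physical examination, and clinical laboratory evaluations" (Protocol 7.5.4, repeated in 7.6.3). Protocol 7.5.4.8 has clinically significant laboratory changes recorded as AEs. SAP 8.9.1 treats an AE as treatment-emergent if it was absent before the first dose in this study, or was present then and became more severe.

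Under SAP 5.3, Rollover subjects keep their CL201 baseline. Non-Rollover subjects use values up to Month 0 of CL202, and no value from before their first UX007 dose is available.

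**The concern.** CL202 has no control arm, so a laboratory percentage is informative mainly by comparison with the same subject's earlier values. The planned percentage makes no such comparison. A subject whose ALT was above range at baseline and stays there unchanged is counted as abnormal after dosing, exactly like a subject whose ALT rose during treatment. The count is also cumulative, so it can only rise as visits accrue.

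Abnormal baseline values are plausible here. Protocol 7.3.2 sets no laboratory limit for entry beyond the investigator's judgement of risk, up to three antiepileptic drugs are allowed, and Protocol 7.5.4.4 does not require fasting samples, which matters for glucose.

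At stake is whether the report can say what changed. SAP 8.8 plans change from baseline for the CNS and SF scores of Rollover subjects, but SAP 8.9.2 plans none for laboratory values, although safety is the primary objective.

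**Working it through.** The documents state no figure on this point, so there is none to reproduce. The check has a textual part and an illustrative part.

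**Text.** Four features would separate new from old abnormalities: a normal-baseline condition, a worsening rule, a grade, or confirmation. The counting rules in SAP 4.1, SAP 8.9.2 and Protocol 7.6.3 contain none of them. The clinically significant category adds a second kind of abnormality but no baseline condition, and and/or leaves open whether the two kinds are counted together or apart.

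**Inputs for size.**
- Post-baseline draws: 8 (Months 3, 6, 9, 12, 18, 24, 30, 36), from the Schedule of Events.
- Subjects: up to 40 (SAP 3.5).
- Assumed, not in the documents: chance out-of-range rate per test p = 1% to 5%; within-subject correlation from 0 to 1.

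**Chance abnormalities, independent draws.** P(at least one) = 1 − (1 − p)^k.
- p = 5%, k = 8: 1 − 0.95^8 = 33.7%, or 13.5 of 40.
- p = 1%, k = 8: 1 − 0.99^8 = 7.7%, or 3.1 of 40.
- p = 5%, Year 1 only (k = 4): 1 − 0.95^4 = 18.5%, or 7.4 of 40.

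With perfectly correlated draws the result is p itself, 1% to 5%.

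**Correlated draws.** Simulation of 500,000 subjects with normally distributed values, p = 5% two-sided, baseline plus 8 visits (the zero-correlation row is exact):

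| Correlation | Counted by the SAP rule | Of those counted, abnormal at baseline | Counted, among those normal at baseline | Abnormal on at least 2 of 8 visits (all subjects) |
|---|---|---|---|---|
| 0 | 33.7% | 5.0% | 33.7% | 6% |
| 0.3 | 29.9% | 7.8% | 29.0% | 7% |
| 0.5 | 25.1% | 12.5% | 23.1% | 9% |
| 0.7 | 19.0% | 20.2% | 16.0% | 9% |
| 0.9 | 11.9% | 38.1% | 7.7% | 8% |

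**Adding persistent abnormality.** Suppose 10% of subjects are abnormal throughout, from baseline on, and the rest have independent chance results.
- p = 5%: SAP rule 0.10 + 0.90 × 0.337 = 40.3%, or 16.1 of 40. Normal at baseline and later abnormal: 40 × 0.90 × 0.95 × 0.337 = 11.5 subjects.
- p = 1%: SAP rule 0.10 + 0.90 × 0.0773 = 17.0%, or 6.8 of 40. Normal at baseline and later abnormal: 40 × 0.90 × 0.99 × 0.0773 = 2.8 subjects.

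**What a baseline condition achieves.** It removes the pre-existing part only. Under independence, the chance rate among subjects normal at baseline is still 33.7% (p = 5%) or 7.7% (p = 1%). Requiring at least two abnormal results in 8 lowers the rate among all subjects, for p = 5%, to 1 − 0.95^8 − 8 × 0.05 × 0.95^7 = 5.7%.

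**The case against.** The best defence is that the plan does have a baseline-referenced route. Clinically significant laboratory changes become AEs, the treatment-emergent rule considers status before the first dose in this study, severity is graded by CTCAE where possible, and grade 3/4 events are summarised. This is a real safeguard, and a reader who inferred that the plan never relates laboratory changes to earlier status would be wrong. It does not close the gap. It depends on the investigator judging the change significant. Its reference is the first CL202 dose, so an abnormality that appeared during CL201 and then stayed the same is not treatment-emergent. It also leaves the laboratory table as it is.

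Four other stronger readings are tempting and not supported:
- *The SAP contradicts the protocol's definition of laboratory safety.* Protocol 7.5.4 describes AEs and SAEs, including clinically significant changes from baseline; it does not define laboratory safety as change from baseline. The laboratory paragraph in Protocol 7.6.3 has the same counting rule as the SAP.
- *The table presents these abnormalities as effects of UX007.* SAP 8.9 plans no statistical comparison of safety data, and 8.9.2 attributes nothing to the drug. The difficulty is one of interpretation, not of error rates.
- *The subject's own baseline is the only possible reference.* Protocol 7.2 allows data from earlier studies and medical records as a comparator.
- *The 33.7% measures pre-existing abnormality.* It measures chance results in unaffected people, under assumed rates.

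It can also be said that shift tables are already intended, because SAP 8.9.2 says results will be shown in them and SAP 7.2.5 mentions them. The first statement sits in the Hy's Law paragraph and is followed only by Hy's Law categories; the second is a data-inclusion rule that names no analyte. Even on the wider reading, the percentages would be counted in the same way. Finally, raw data are listed and values are summarised by visit, so a reader could trace individual subjects. That is possible with up to 40 subjects, but it does not replace a summary.

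**Conclusion.** The point holds as a gap in presentation of moderate weight. The planned laboratory percentages cannot distinguish pre-existing from new or worsened abnormalities, and no general laboratory output in SAP 8.9.2 supplies the missing comparison. This follows from the text and needs no numerical assumption.

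The size is illustrative. The range of 7.7% to 33.7% of subjects per analyte under independence, and 1% to 5% under perfect correlation, rests on an assumed chance rate of 1% to 5% per test and on every subject giving all 8 post-baseline samples. Treatment may stop sooner, for example on commercial availability (Protocol 7.4.4.1), which would lower the figures; extra samples allowed by Protocol 7.5.4.4 would raise them. The documents give neither the rates nor the correlations, and nothing from which to estimate how many subjects start with an abnormal value.

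**What to change.** In SAP 8.9.2, for each analyte, add:
- a shift table from baseline to worst post-dose value, by CTCAE grade where one exists and otherwise by low/normal/high;
- change from baseline by visit;
- the incidence of emergent abnormality, defined as worse than baseline, showing separately those that rise in CTCAE grade or are seen on at least two visits. A normal-to-abnormal rule alone would leave chance results in the count.

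Show clinically significant abnormalities separately from out-of-range results. Use the CL201 baseline for Rollover subjects, and footnote that this reference differs from the one in the TEAE rule. Report Non-Rollover subjects separately, as SAP 8.1 generally plans, against Month 0 labelled as an on-treatment value, and note that this may hide effects of earlier UX007. Keep the planned any-abnormality table as supportive.

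The cost is SAP wording and a few standard tables. No new samples or visits are needed.

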8.9.3 Vital Signs

The following vital signs and weight will be summarized by time point.

- Temperature ($^{\circ}\text{C}$)
- Respiration Rate (breaths/min)
- Heart Rate (beats/min)
- Systolic Blood Pressure (mmHg)
- Diastolic Blood Pressure (mmHg)
- Weight (kg)

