5.2.3 Previous Clinical Studies

Approximately 200 subjects with various diseases have been treated with triheptanoin for periods of up to 15 years. Of these subjects, approximately 50 were pediatric patients as young as neonates; a significant portion of pediatric patients had treatment duration of over 5 years. The clinical experience supports the safety of triheptanoin when administered at approximately 35% of daily caloric intake in pediatric patients as young as neonates.

Triheptanoin has been studied for over a decade in a large cohort of patients with fatty-acid oxidation disorders (FAOD) as part of a compassionate use program (Roe et al. 2002), (Roe et al. 2006), (Roe et al. 2008), (Barone et al. 2012). Ultragenyx is currently developing UX007 as a substrate replacement therapy for long-chain FAOD (LC-FAOD).

Patients with other disorders have also been treated with triheptanoin, including those with pyruvate carboxylase deficiency (Mochel et al. 2005), Huntington's disease (Mochel et al. 2010), adult polyglucosan body disease (APBD) (Roe et al. 2010), glycogen storage disease

type II (GSD-II; Pompe disease) (Roe et al. 2006) and congestive heart failure (IND 65827). Triheptanoin treatment has been generally safe and well tolerated in subjects with these disorders.

Triheptanoin was studied in 14 Glut1 DS subjects (including 11 pediatric subjects) in a clinical trial sponsored by [name] at the University of Texas, Southwestern. The results of this open-label study suggest clinical activity with triheptanoin in reducing the frequency of absence seizures (Pascual et al. 2014). No patient experienced serious or unexpected adverse events (AE). One patient (7%) discontinued triheptanoin therapy after 3 weeks owing to gastric discomfort. One other patient (7%) experienced significant (10%) weight gain at 2 months that did not lead to discontinuation. This patient did not follow recommended dietary and nutritional advice to decrease extra sources of fat and simple sugars. Two patients (14%) experienced diarrhea and/or digestive discomfort within days of treatment initiation; symptoms resolved by reducing the triheptanoin dose by one-half and gradually increasing the amount to the target levels over several days.

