Data from nonclinical and clinical studies to date suggest triheptanoin does not pose any serious safety risks that can be identified at this time. Triheptanoin has been well tolerated in humans with no significant safety issues and toxicology or adverse pharmacology findings were not observed in triheptanoin-treated animals. Studies in animals and humans suggest triheptanoin consumed orally has side effects that are similar to those of orally consumed medium chain triglycerides (MCT oil). The most commonly reported adverse effects are gastrointestinal distress and excessive weight gain at high doses. Both of these issues appear to resolve when triheptanoin is consumed in small doses mixed with foods throughout the day and when total caloric intake is appropriately managed. Overall the risk-benefit ratio of UX007 is sufficient to support clinical development for the treatment of seizures associated with Glut1 DS.

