7.4.4.1 Study Duration

The planned duration of treatment in this study is 3 years, or until one of the following occurs: the subject withdraws consent, the subject is discontinued from the study at the discretion of the Investigator or Ultragenyx, the study is terminated, or until commercial availability of study drug in a subject's region, whichever occurs first. The length of the study is intended to define whether UX007 is safe for long-term use and provide sufficient insight on sustained clinical effects. A Safety Follow-up Phone Call will be conducted 30-35 days after last dose of study drug. The last subject's Safety Follow-up Phone Call is the End-of-study Time Point.

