Descriptive statistics of temperature, pulse, respiratory rate, and blood pressure (systolic and diastolic) values and changes from baseline will be summarized. The percentage of subjects with values beyond clinically important limits will be summarized.

The SAP will provide additional details on the planned safety analyses.

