3.1 Study Population

The study will be conducted in pediatric, adolescent, and adult Glut1 DS patients (aged at least 1 year at the time of informed consent) who have successfully completed the associated Phase 2 study (UX007G-CL201) or, at the discretion of the Sponsor, additional subjects who

participated in other clinical studies, ISTs, or expanded access/compassionate use treatment programs. Enrollment may include subjects from neighboring countries where clinical sites are located. Appropriate local or country requirements will be followed. All subjects in this study will have prior treatment exposure to UX007/triheptanoin. Refer to the protocol for detailed inclusion and exclusion criteria.

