3.5 Sample Size Considerations

This study will enroll up to 40 pediatric, adolescent, and adult Glut1 DS subjects who have completed the UX007G-CL201 study and, at the discretion of the Sponsor, additional subjects from participated in other clinical studies, ISTs, or expanded access/compassionate use treatment programs. The sample size is intended to provide the maximum amount of information regarding UX007 long-term safety, along with indicators of sustained efficacy and durability of response in Glut1 DS patients.

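### Weight is summarised only in observed kilograms by visit, so the weight table cannot tell excess gain from normal growth or a changing age mix

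*SAP*

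**What the plan says.** SAP 4.1 lists the safety endpoint as "Observed value of vital signs and weight during the study". SAP 8.9.3 then states "The following vital signs and weight will be summarized by time point" and lists weight in kg beside temperature, respiration, heart rate and blood pressure. Neither section plans a change from baseline, a percent change, an age- and sex-standardised score, a count above a threshold or an age split for weight. The only general split is Rollover versus Non-Rollover (SAP 8.1).

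The protocol aims further. Sections 7.5.4 and 7.6.3 say safety is evaluated through clinically significant changes from baseline to scheduled time points, and both name weight. The sentence in 7.6.3 that specifies statistics does not: "Descriptive statistics of temperature, pulse, respiratory rate, and blood pressure (systolic and diastolic) values and changes from baseline will be summarized".

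On the risk itself, Protocol 5.3 says "The most commonly reported adverse effects are gastrointestinal distress and excessive weight gain at high doses". Protocol 5.2.3 reports, from the earlier open-label trial in 14 Glut1 DS subjects, "One other patient (7%) experienced significant (10%) weight gain at 2 months that did not lead to discontinuation".

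On population and follow-up, subjects are "aged at least 1 year at the time of informed consent" (SAP 3.1) with no upper age limit, "This study will enroll up to 40 pediatric, adolescent, and adult Glut1 DS subjects" (SAP 3.5), and "The planned duration of treatment in this study is 3 years" (Protocol 7.4.4.1) unless an earlier end point applies.

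**The concern.** Over 3 years a growing child should gain weight, so a rising mean in kg is expected without any drug effect. The mean also moves when the subjects contributing to a visit change. One exit route, commercial availability in a subject's region, has nothing to do with weight but can alter the age mix at later visits. A table of observed kg by visit mixes growth, age mix and any excess gain, and gives the reader no means of separating them. A flat mean is no more reassuring than a rising one is alarming.

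Long-term safety is the primary objective, and excess weight gain is one of two adverse effects that Protocol 5.3 names as most common. The other, gastrointestinal distress, has its own standardised MedDRA query summary (SAP 4.1, 8.9.1 and Appendix C). Weight gain has no dedicated analysis, and the protocol's intention to look at change from baseline in weight does not reach the SAP's measured-data tables.

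**Working it through.** The documents state no figure that depends on weight, so there is none to reproduce. The first step compares texts; the rest are illustrations on stated assumptions.

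**1. Protocol against SAP.** Protocol 7.5.4 and 7.6.3: change from baseline in weight is part of the safety evaluation. SAP 4.1: observed value. SAP 8.9.3: summary by time point, in kg. The change is not carried through.

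**2. Growth alone.** Assumptions, not in the documents: a 20 kg child growing g = 2-3 kg a year.
- Gain over 3 years = 3g = 6-9 kg; divided by 20 kg, 30-45%.
- A 10% excess over the expected weight of 26-29 kg is 2.6-2.9 kg. Its share of total gain is 2.6/(6 + 2.6) = 30% to 2.9/(9 + 2.9) = 24%.
- With wider assumptions (12-35 kg at baseline, 2-5 kg a year) the 3-year excess is 1.8-5.0 kg, or 15-41% of total gain.

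**3. The 10% gain in the earlier trial.** It was seen at 2 months.
- In a 20 kg child it is 2 kg.
- Growth over 2 months = g x 2/12 = 0.33-0.5 kg, or 1.7-2.5%.
- The gain is 2/0.5 = 4 to 2/0.33 = 6 times expected growth, so it would be plain in that child's own data.
- In the mean of 40 subjects, one such gain adds 2/40 = 0.05 kg.

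**4. Changing mix.** Assumption: between-subject SD of weight 15-25 kg across ages 1 year to adult. If one subject lying one SD from the mean leaves a group of 40, the mean moves by SD/39 = 0.38-0.64 kg. That is about 8 to 13 times the 0.05 kg in step 3.

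**5. Precision of a visit mean.** The 95% half-width is 1.96 x SD/√N. With N = 40 and SD 15-25 kg it is 4.6-7.7 kg, larger than most of the 1.8-5.0 kg range in step 2. N = 40 is the maximum, and the Rollover split makes each group smaller. A paired change in the same subjects would be more precise, but none is planned. Even a precise mean in kg would still contain the growth in step 2.

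**6. Baseline for Rollover subjects.** SAP 5.3 takes their baseline from CL201. If entry follows directly on that study's Week 52 visit, change from baseline at Month 36 spans about 4 years: 4g = 8-12 kg, or 40-60% of 20 kg, from growth alone. A change in kg would therefore need age standardisation to be interpretable in children.

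**The case against.** The strongest case on the other side is that the weight table is only supportive. The primary endpoint is AEs and SAEs. Protocol 7.5.4.2 and 7.5.4.8 require clinically significant weight changes to be recorded as AEs; these are graded and tabulated by preferred term (SAP 8.9.1). All raw CRF data are listed (SAP 8.1), and with at most 40 subjects each child's weights can be read directly. Study-drug and total daily calories are summarised by visit (SAP 8.7.3). Protocol 5.3 ties the risk to high doses and says it appears to resolve with small, divided doses and managed calories. Protocol 5.2.3 adds that the subject who gained 10% had not followed dietary advice. The summary could also be produced later from weights already collected.

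Most of this stands, and it rules out three stronger readings that a reader might infer:
- That weight gain is hidden from the safety data. It is not: the AE tables and listings remain.
- That a 10% gain could not be seen at all because it resembles a year of growth. The reported gain took 2 months, several times the growth assumed here, and would show in an individual's data.
- That better weight analysis would isolate the drug's effect. In a single-arm study a z-score separates gain from reference growth only; it cannot attribute the excess to drug, diet or other care.

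The objection does not rescue the table. The AE route depends on investigator judgment with no stated threshold. A weight-gain event already present at the first CL202 dose counts as treatment-emergent only if it worsens (SAP 8.9.1), and every subject has prior exposure. Reading listings by eye is not a prespecified analysis, and choosing a cut after seeing open-label data is weaker than fixing it beforehand.

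**Conclusion.** The point holds for the weight summary. As planned, it cannot distinguish excess gain from normal growth or a shifting age mix, and it leaves out the change from baseline in weight that the protocol intends to evaluate. On the assumed growth rates, growth alone accounts for a 30-45% rise over 3 years in a 20 kg child.

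The growth rates, starting weights and SDs are assumptions, and the documents give no age distribution. The conclusion needs only that a meaningful share of subjects are still growing. Adults are not affected by growth, but they too have no change score. No planned estimate becomes invalid and no data are lost; this is an inexpensive improvement worth making before analysis.

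**What to change.** In SAP 4.1 and 8.9.3, keep the kg table and add:
- for children and adolescents, change from baseline in weight-for-age-and-sex z-score, from a growth reference that the SAP names and that covers the ages enrolled, with a rule for subjects who pass its upper age during follow-up;
- for adults, percent change in weight;
- both from CL202 Month 0 and, for Rollover subjects, also from the CL201 baseline;
- n (%) above a cut fixed before analysis, as a reporting threshold only and not a rule for managing subjects;
- a sentence that results show gain relative to reference growth, not gain attributed to the drug.

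No new visits or measurements are needed. Weight is taken at every clinic visit, and SAP 5.5 and 8.4 already use birth date and gender. For Rollover subjects the CL201 weights must be available to the analysis. The cost is SAP wording, programming and one more table.

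Two downsides remain. Splitting at most 40 subjects by age group and Rollover status leaves small cells. Weight-for-age does not separate height from adiposity: height appears only as a Columbia Neurological Score domain worth at most 1 point (SAP 5.9), so a BMI-based score is possible only if the measured height is recorded.
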